Comparison of surgical outcomes between end-to-side and side-to-side anastomosis after laparoscopic right hemicolectomy: a prospective randomized controlled trial

Version No: 1.0

Principal Investigator Affiliation: Bundang Seoul National University Hospital

Principal Investigator Name: [name]

Confidentiality: All information contained in this research protocol is provided for the principal investigator, research staff, and the Institutional Review Board. Except for obtaining written consent for research participation, this information may not be disclosed to any third party without prior written consent from Bundang Seoul National University Hospital.

Study Overview

Study Title	Comparison of surgical outcomes between end-to-side and side-to- side anastomosis after laparoscopic right hemicolectomy: a prospective randomized controlled trial
Principal Investigator	[name], Department of Surgery, Bundang Seoul National University Hospital
Funding Institution	Bundang Seoul National University Hospital (In-House Research Project: 14-2016-016)
Study Objective	There is ongoing debate regarding the relationship between anastomotic techniques and surgical outcomes (such as recovery period and complications). To date, no prospective randomized clinical study has been reported comparing postoperative outcomes between end-to-side and side-to-side anastomosis following right hemicolectomy. This study aims to establish a standard anastomotic method after right hemicolectomy.
Study Design	a single center prospective randomized controlled trial
Study Duration	IRB Approval Date – June 30, 2018
Study Subjects	Patients scheduled for laparoscopic right hemicolectomy for right-sided colon cancer at Bundang Seoul National University Hospital.
Number of Study Subjects	130 patients (65 in the end-to-side anastomosis group, 65 in the side-to-side anastomosis group).
Vulnerable Study Subjects	Not applicable.
Investigational Drug/Medical Device	Not applicable.
Dosage and Administration	Not applicable.
Study Method	After random allocation of the anastomotic technique during surgery, a comparative analysis will be conducted between the two groups on cumulative recovery rate, length of hospital stay, complications, failure rate of the early recovery program, and readmission rate within one month after surgery.
Inclusion Criteria	
 Patients scheduled for laparoscopic right hemicolectomy for right-sided colon cancer Patients who will undergo an early recovery program after surgery
Exclusion Criteria	
 Cases where laparoscopic surgery is not feasible due to a history of abdominal surgery or the severity of the disease Individuals who do not consent to the study
Efficacy Assessment	
 Primary Outcome Variable: 7-day cumulative recovery rate Secondary Outcome Variables: Length of hospital stay, complications, failure rate of the early recovery program, and readmission rate within one month after surgery
Safety Assessment	All adverse events occurring in both groups (end-to-side anastomosis group and side-to-side anastomosis group) will be investigated, and an assessment will be made to determine which group experiences a higher occurrence.
Tests/Visit Schedule	Not applicable.
Statistical Analysis	
The statistical analysis will be conducted using SPSS. A p-value of ≤ 0.05 will be considered statistically significant.
 
Continuous variables: Student's t-test, Mann-Whitney U test
 
Binary variables: χ^2-test, Fisher's exact test

Expected Benefits and Anticipated Outcomes	
• This study may help establish a standardized anastomotic technique following right hemicolectomy.• It can provide scientific evidence for the optimal anastomotic method after colectomy, which may also be applicable to other gastrointestinal resections.• This research can serve as a foundation for expanding beyond a single-center study to a multi-center study.
---	---

Research Protocol

1. Study title: Comparison of surgical outcomes between end-to-side and side-to-side anastomosis after laparoscopic right hemicolectomy: a prospective randomized controlled trial

2. Name and Address of the Research Institution

- 1) **Name of Research Institution:** Bundang Seoul National University Hospital
- 2) **Address:** [name]

3. Name and Title of Principal Investigator and Co-Investigators

1) **Principal Investigator:** [name], Professor, Department of Surgery, Bundang Seoul National University Hospital.

2) **Co-Investigators:**

- **[name]**, Associate Professor,
Department of Surgery, Bundang Seoul National University Hospital
- **[name]**, Associate Professor,

The authors previously reported that, when an early recovery program was applied after laparoscopic right hemicolectomy for right-sided colon cancer, the end-to-side anastomosis group had a higher cumulative recovery rate on postoperative day 7 (71.7% vs. 93.0%, $p = 0.019$), a shorter length of hospital stay (7 vs. 6 days, $p = 0.003$), and a lower complication rate (26.1% vs. 4.6%, $p = 0.008$) compared to the side-to-side anastomosis group (7). Another study reported that side-to-side anastomosis was a major factor contributing to early recovery program failure in patients, including those with not only right-sided colon cancer but also left-sided and sigmoid colon cancer (8).

2) Hypothesis and purpose

Currently, there is no established standard anastomotic technique for laparoscopic right hemicolectomy. End-to-side anastomosis is considered anatomically ideal, and it is hypothesized that it may result in superior short-term outcomes. This study aims to demonstrate the superiority of end-to-side anastomosis through a prospective randomized comparative study between end-to-side and side-to-side anastomosis.

9. Investigational Drug and Medical Device Code Name (or Generic Name of Active Ingredient), Quantity of Active Ingredient, Dosage Form (Including Comparator) : Not applicable.

10. Selection Criteria, Exclusion Criteria, Target Sample Size, and Rationale for Sample Size Calculation

1) Selection Criteria:

Subjects must meet all of the following conditions:

① Patients with right-sided colon cancer

Right-sided colon cancer is defined as tumors located from the cecum to the hepatic flexure. The histological type is limited to adenocarcinoma.

- ② Patients aged between 18 and 80 years
- ③ Patients with adequate bone marrow function:
Hemoglobin ≥ 10 g/dL (in cases of simple iron deficiency anemia, correction is required)
White blood cell count $\geq 4,000/\text{mm}^3$
Platelet count $\geq 100,000/\text{mm}^3$
- ④ Patients with adequate renal function (Creatinine ≤ 1.5 mg/dL)
- ⑤ Patients without significant functional impairment of the heart, lungs, or other major organs
- ⑥ Patients who have signed the written informed consent form

2) Exclusion Criteria

Patients who meet any of the following conditions will be excluded from this clinical trial:

- ① **Patients with distant metastasis or local invasion to the small intestine, ureter, or other adjacent structures requiring combined resection**
- ② **Patients in whom laparoscopic surgery is not feasible due to a history of prior abdominal surgery or the severity of the disease**
- ③ **Patients requiring emergency surgery due to bowel obstruction or peritonitis**
- ④ **Patients taking other oral medications for bowel movement disorders, such as chronic constipation, before surgery**
- ⑤ **Patients with severe cardiopulmonary disease, mental illness, or other comorbidities that prevent the application of the early recovery program**
- ⑥ **Patients who do not consent to the study or do not sign the informed consent form**
- ⑦ **Patients deemed ineligible for clinical trial participation based on the physician's judgment**

3) Target Sample Size and Rationale for Sample Size Calculation

This study aims to evaluate the superiority of end-to-side anastomosis over side-to-side anastomosis in terms of short-term outcomes. The sample size was calculated based on previous studies (7,9).

Allocation ratio: 1:1

Type I error (α): 5%

Power: 80%

Expected difference in 7-day cumulative recovery rate: 20% (End-to-side: 90% vs. Side-to-side: 70%)

Expected dropout rate: 10%

The calculated sample size is as follows:

◆ Target number of participants: 130

End-to-side anastomosis group: 65 participants

Side-to-side anastomosis group: 65 participants

(The sample size will be further reviewed and adjusted upon consultation with the Clinical Research Institute at Seoul National University.)

◆ Randomization

The **allocation ratio** between groups will be **1:1**.

The anastomosis method will be determined preoperatively using a **random table or computer-generated randomization program**.

Group allocation will be revealed **in the operating room just before anastomosis**.

(The randomization process will be conducted in consultation with the Clinical Research Institute at Seoul National University.)

4) Recruitment Plan

There will be **no public recruitment announcement** for participant enrollment. Instead, patients admitted for **laparoscopic right hemicolectomy** for right-sided colon cancer will be provided with detailed information about the study, including its objectives, safety, and potential risks. After obtaining written informed consent, eligible patients will be enrolled in the study.

11. Study methods

1) Detailed methods

(1) Design

: Prospective randomized clinical trial

(2) Classification of Patient Groups

① **Patient group classification will be revealed just before surgery.**

② **Patients will be randomly assigned into two groups: the end-to-side anastomosis group and the side-to-side anastomosis group.**

③ **Except for the anastomotic method, all other procedures will be conducted identically in both groups.**

[figure not shown]

Figure 1. Schematic Diagram of Side-to-Side Anastomosis (a) and End-to-End Anastomosis (b)

(3) Postoperative Management

① **All patients participating in the study will undergo the Enhanced Recovery Program (ERP) after surgery.**

② **The ERP protocol applied will be based on the protocol used in the researchers' previous studies.**

③ **If complications such as ileus or obstruction occur during the application of the ERP, the program will be immediately discontinued, and appropriate examinations and treatments will be administered at the physician's discretion. In such cases, it will be considered a failure of the ERP application.**

Operative day	diet		exercis
Operative day	Sow of water	
 After 4 hours of arrival in the hospital room from the operating room, initiate oral intake after confirmation by the attending medical staff. Start with small sips to moisten the mouth and gradually increase the intake instead of consuming a large amount at once. However, the total dietary intake should not exceed 1 liter per day. If symptoms such as nausea, vomiting, or abdominal pain occur, discontinue oral intake and perform necessary examinations and treatments. 	
 Sit for a total of 1 hour per day. Spend at least one hour per day out of bed. Sitting can be divided into 4 sessions of 15 minutes each or 6 sessions of 10 minutes each. Various options are allowed, such as sitting on the edge of the bed or sitting on the caregiver's bed.
Postoperative Day 1	Liquid diet (three times a day)	
 Like water, liquid food should be consumed in small amounts initially and gradually increased rather than taken in large quantities at once. There is no strict limitation on the amount, but if symptoms such as nausea, vomiting, or abdominal pain occur, discontinue intake and perform necessary examinations and treatments. 	
 Sit for a total of 3 hours per day. Walk in the hospital corridor. If walking alone is difficult, assistance from a caregiver or the use of a walker is allowed.
Postoperative Day 2	Soft porridge (three times a day)	There is no strict limitation on the amount, but if symptoms such as nausea, vomiting, or abdominal pain occur, discontinue the diet and perform necessary examinations and treatments.	Walking in the hospital corridor: Walk back and forth along the corridor at least three times. If walking alone is difficult, assistance from a caregiver or the use of a walker is allowed.
After Postoperative Day 2	Soft porridge (three times a day)	There is no strict limitation on the amount, but if symptoms such as nausea, vomiting, or abdominal pain occur, discontinue the diet and perform necessary examinations and treatments.	Walking in the hospital corridor: Walk back and forth along the corridor at least three times. If walking alone is difficult, assistance from a caregiver or the use of a walker is allowed.

Table 1. Implementation of the Early Recovery Program

(4) Data Collection Items

- ① **Basic patient data** (age, sex, body mass index, medical history, ASA grade)
- ② **Preoperative staging** (CT, endoscopic findings)
- ③ **Intraoperative findings** (operative time, intraoperative blood loss)
- ④ **Postoperative course** (gas out time, length of hospital stay, recovery time, occurrence of complications)
- ⑤ **Histopathological results and staging**
- ⑥ **Readmission within one month after surgery and its reason**

2) Control Group Setting and Randomization Method

A comparison will be made between end-to-side anastomosis and side-to-side anastomosis.

Randomization will be conducted using the **SAS program**, managed by the **MRCC at Bundang Seoul National University Hospital**. A random number will be generated, assigned a serial number, and the anastomotic method will be delivered just before surgery to ensure random allocation.

3) Investigational Drug Administration/Usage, Method of Administration, Concomitant Therapy, and Justification for Comparator Use

Not applicable.

4) Observation Items, Clinical Examination Items, and Evaluation Methods for Study Outcomes

(1) Primary Endpoint: 7-Day Cumulative Recovery Rate

The **cumulative recovery rate** is defined as the percentage of patients who have reached **recovery time** within a specific postoperative period.

The definition of **recovery time** is based on previous studies by the investigators (7, 9) and is defined as the postoperative time at which **all** of the following conditions are met:

- ① **No issues for 24 hours after diet initiation** (at least one-third intake of liquid diet or higher).
- ② No additional analgesic administration after discontinuation of patient-controlled analgesia (PCA).
- ③ No major complications and stable afebrile condition (body temperature $\leq 37.2^{\circ}\text{C}$).
- ④ No issues with ambulation (ability to walk a distance of at least 600 meters).

(2) Secondary Endpoint

- **Length of hospital stay**
- **Complications**
- **Failure rate of the early recovery program**
- **Readmission rate within one month after surgery**

5) Criteria and Methods for Efficacy Evaluation

This study evaluates the superiority of end-to-side anastomosis over side-to-side anastomosis in terms of short-term outcomes. The sample size was calculated based on previous studies (7,9).

- **Allocation ratio:** 1:1
- **Type I error (α):** 5%
- **Power:** 80%
- **Expected difference in 7-day cumulative recovery rate:** 20% (End-to-side: 90% vs. Side-to-side: 70%)
- **Expected dropout rate:** 10%

The hypothesis to be tested is that the **cumulative recovery rate** in the end-to-side anastomosis group is 20% higher than in the side-to-side anastomosis group.

6) Differences from Existing Treatments and Studies

Both **end-to-side and side-to-side anastomosis** are standard anastomotic techniques commonly used in clinical practice, meaning that this study does not involve a new or experimental treatment. However, research specifically comparing **anastomotic techniques in right-sided colon cancer** is limited, with most existing studies being retrospective cohort studies. Thus, this study will be the first prospective, randomized controlled trial investigating anastomotic methods in right-sided colon cancer.

7) Benefits and Risks for Study Participants

Since this study compares two **existing standard anastomotic techniques**, there are minimal risks or additional benefits associated with participation. Furthermore, the scientific and medical knowledge gained from this research is expected to far outweigh any potential risks or **adverse effects** experienced by study participants.

8) Discontinuation and Withdrawal Criteria

- ① Conversion to open surgery during the procedure due to safety concerns that make continued laparoscopic surgery unsafe for the patient.
- ② Participants who initially consented to the study but later decide to withdraw their consent.

9) Criteria, Methods, and Reporting for Adverse Events and Safety Evaluation

- ① This study compares **two standard and well-established anastomotic techniques** that are already considered safe and routinely used in clinical practice, even for patients who are not part of the study. **Therefore, the likelihood of adverse events resulting directly from participation in this study is expected to be minimal.**
- ② **Even if a patient experiences postoperative side effects or complications, these are not caused by participation in the study but are general complications that can occur after laparoscopic right hemicolectomy. The presence or absence of such complications is also one of the comparison/evaluation criteria in this study.**

10) Data Safety Monitoring Plan (DSMB)

(1) Monitoring Supervisor

- **[name] (Principal Investigator, Professor of Surgery, Bundang Seoul National University Hospital)**

(2) Monitoring Frequency

- **Monitoring will be conducted when the 40th and 100th participants are enrolled.**

(3) Monitoring Method

- **Under the supervision of the monitoring supervisor, monitoring personnel will review essential documents and cross-check medical records for one participant.**

(4) Handling of Findings During Monitoring

- The monitoring supervisor will determine the type and severity of findings in the monitoring report and may request reporting to the Institutional Review Board (IRB), implementation of corrective actions, and measures to prevent recurrence.

(5) Reporting Procedures to the Institutional Review Board (IRB)

A. The monitoring report must be submitted to the IRB as an "Other Report" by the principal investigator.

B. Deadline for IRB reporting of findings identified during monitoring:

- Adverse Drug/Medical Device Reaction Reports (Fatal/Life-Threatening Cases):
 - Initial report within 7 days + Follow-up report within 8 days
- Adverse Drug/Medical Device Reaction Reports (Non-Fatal/Non-Life-Threatening Cases):
 - Other cases (hospitalization or prolonged hospitalization, persistent or significant disability, congenital anomalies, significant medical events, etc.) must be reported within 15 days.
- Safety Information Report: Once every 6 months
- Unexpected Problem Report: Within 15 days
- Major Noncompliance Report: Within 15 days
- Minor Noncompliance Report: Once every 6 months

(6) Review of Key Efficacy Evaluation Variables for Decisions on Study Continuation, Modification, or Termination

A. No interim analysis will be conducted for efficacy evaluation.

B. Safety review will be conducted as follows to determine study modification or termination:

- If a serious and unexpected adverse event occurs:
 - (A) The principal investigator will review the event and decide on study modification or termination.
 - (B) If the IRB review results in a decision to modify or terminate the study, the research team will comply with the IRB's directive.
- Safety review will be conducted once every 6 months:
 - (A) The principal investigator will review all adverse events that occurred in the past 6 months and determine whether study modification or termination is necessary.
 - (B) The findings reviewed in section (A) will be reported as an "Other Report" to the respective Institutional Review Board (IRB) of each institution.

11) Data Analysis and Statistical Methods

- Statistical analysis will be conducted using SPSS or STATA. A p-value of ≤ 0.05 will be considered statistically significant.
 - Continuous variables: Student's t-test, Mann-Whitney U test
 - Binary variables: χ^2 -test, Fisher's exact test
- If advanced statistical analysis techniques are required, consultation with the Medical Research Institute will be sought for expert statistical guidance and analysis.

12) Study Schedule

Contents	Duration											
	2	4	6	8	10	12	14	16	18	20	22	24
IRB Review	■											
Selection of Study Participants and Obtaining/Registration of Informed Consent		■	■	■	■	■	■	■				
Data collection			■	■	■	■	■	■				
Statistical analysis									■	■		
Final Report										■	■	
Final Research Paper										■	■	

12. Measures for the Protection of Study Participants' Safety

1) Basic Measures to Ensure Ethical Conduct of the Study

- The study will comply with the Declaration of Helsinki (2013 revision) and ICH-GCP guidelines.
- The study will be conducted only after obtaining IRB approval.

2) Informed Consent Process for Study Participants

- ① Researchers responsible for explaining the study and obtaining consent: A physician among the research team.
- ② Individuals providing consent: Study participants.
- ③ Waiting period between study explanation and consent acquisition: 20 minutes.
- ④ Methods to minimize coercion or undue influence:
 - a. The researcher (usually the attending physician) will explain the study to the participant.
 - b. The research coordinator will provide additional explanations in a separate space.
 - c. The researcher will confirm if the participant has any additional questions before obtaining consent.

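### The protocol gives two different times for revealing the allocation; under the earlier one the operating team can know the arm when conversion to open surgery, a withdrawal criterion, is decided

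*Combined protocol and SAP*

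**What the plan says.** Four places in the combined protocol and SAP bear on when the arm becomes known.

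- Section 10.3, Randomization: the group is revealed "in the operating room just before anastomosis". The same paragraph says "The anastomosis method will be determined preoperatively using a" random table or a computer program, and adds "The randomization process will be conducted in consultation with the Clinical Research Institute at Seoul National University".
- Section 11.1(2), item 1: "Patient group classification will be revealed just before surgery".
- Section 11.2: "the anastomotic method will be delivered just before surgery to ensure random allocation", with each random number given a serial number.
- Study Overview, Study Method row: random allocation of the technique takes place in the course of the operation.

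Two further statements determine why the timing matters. Section 11.1(2), item 3, states: "Except for the anastomotic method, all other procedures will be conducted identically in both groups". Section 11.8 lists two discontinuation and withdrawal criteria. One is withdrawal of consent; the other is "Conversion to open surgery during the procedure due to safety concerns that make continued laparoscopic surgery unsafe for the patient".

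**The concern.** Sections 10.3 and 11.1(2) answer the same question differently, and the dissection and resection lie between the two answers. Staff who follow 11.1(2) literally would open the assignment before the operation begins. Staff who follow 10.3 would open it only once the bowel is ready to be joined.

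Two things are at stake. The first is that the steps common to both arms are meant to be identical. With a late reveal they are carried out without knowledge of the arm; with an early reveal their equality depends on discipline alone. The second is that conversion rests on a judgement made during the operation and is a route out of the trial. If the arm is known when that judgement is made, it could influence who is withdrawn after assignment.

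A related uncertainty is that the method is fixed before the operation, revealed at one of two times, and governed by a process still to be settled in consultation. The moment at which a patient counts as randomised is therefore not defined.

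**Working it through.** **1. The statements side by side**

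| Place | Event described | Time |
|---|---|---|
| Section 10.3 | group revealed | in theatre, immediately before the anastomosis |
| Study Overview | allocation | during the operation |
| Section 11.1(2) | group revealed | immediately before the operation |
| Section 11.2 | method delivered | immediately before the operation |

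Sections 10.3 and 11.1(2) both speak of revealing, so they conflict directly. Section 11.2 speaks of delivery. A delivered assignment may be open or sealed, so that section fits either time.

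**2. Order of events**

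The Recruitment Plan (10.4) puts information and written consent before enrolment. The order is then: consent; early reveal (11.1(2)); dissection and resection; late reveal (10.3); anastomosis. Both reveals come after consent. They differ only in whether the arm can be known during dissection, resection and any conversion decided before the anastomosis. The documents do not say to whom the group is revealed, and no passage keeps the operating team unaware after an early reveal.

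**3. What can be quantified**

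The documents give no conversion rate and no recovery rate for converted patients. They also do not say whether converted patients leave the analysis. The size and direction of any bias therefore cannot be computed.

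**4. Does the dropout allowance cover the fix?**

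If patients converted before opening are not counted as randomised, and if 130 counts consented patients, fewer than 130 are assigned. Inputs from section 10.3: 90% vs 70%, α 5% (sidedness not stated), power 80%, dropout 10%. The protocol names no formula, so several were tried.

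- Two-sided, unpooled: n = (1.960 + 0.842)² × (0.9×0.1 + 0.7×0.3) / 0.20² = 58.9, so 59 per arm, 118 in total. 118 × 1.10 = 129.8, which reproduces 130. Dividing instead, 59 / 0.90 = 65.6, so 66 per arm, 132 in total.
- Two-sided, pooled: 61.6, so 62 per arm, 124 in total. 124 × 1.10 = 136.4; 62 / 0.90 = 68.9, so 69 per arm, 138 in total. Neither gives 130.
- One-sided, pooled, continuity-corrected: 58 per arm. 58 / 0.90 = 64.4, so 65 per arm, 130 in total.

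The two two-sided formulas leave reserves of 130 − 118 = 12 and 130 − 124 = 6 patients. On an assumed 3% to 9% conversion before opening, 130 × 0.03 = 3.9 to 130 × 0.09 = 11.7 patients would not be assigned. That fits within 12 but, at the upper end, not within 6. At 59 per arm, two-sided power is 80.1% unpooled and 78.2% pooled. Whether the allowance covers the loss thus depends on a formula and a rate that the protocol does not give.

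**The case against.** The best case against giving this much weight is as follows. Neither time exposes the arm at enrolment. Conversion is tied to patient safety, in wording that does not depend on the arm. Identical procedures are required whichever time is used. Listing conversion as a withdrawal criterion does not say that converted patients leave the analysis. The missing analysis population in the statistics section (11.11) is a gap under either reveal time. Finally, section 10.3 is expressly provisional, while 11.2 names the program and the managing unit, so the documents do not show which time was intended.

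Most of this stands, and it limits the point. A reader might infer that allocation concealment at enrolment is broken; the order of consent and reveal does not support that. A reader might also infer that arm-dependent conversion will occur, or will favour end-to-side because the protocol expects that technique to be superior; nothing in the documents shows either. The handling of converted patients in the analysis is a separate gap, and the choice of the later time is a recommendation.

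The objection does not remove the conflict. A safety judgement is still a judgement, and a rule requiring identical procedures is better protected when the arm is unknown. The later time is already in the protocol and agrees with the Study Overview.

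**Conclusion.** The point holds as an unreconciled conflict over the reveal time, with a plausible but unquantified consequence. The conflict is certain from the text. The consequence is conditional: if 11.1(2) is followed and the operating team is among those told, the shared operative steps and the conversion decision can take place with the arm known. Any resulting bias is of unknown size and direction.

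It would be tempting to add that the 10% dropout allowance absorbs the cost of the fix. That is not claimed, because the answer changes with the sample-size formula and the conversion rate, and the protocol states neither. If 130 means assigned patients, as the split into 65 per group suggests, the question does not arise.

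The point should be corrected, but it is of modest weight and gives no reason to change the sample size.

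**What to change.** State one reveal time throughout.

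- Amend section 11.1(2), item 1, so that the group is revealed "in the operating room just before anastomosis", as in 10.3.
- State in 11.2 that the numbered assignment delivered before the operation stays sealed until that moment.
- State in 10.3 that the sequence is generated beforehand and that a patient counts as randomised when the assignment is opened. This can be settled in the consultation that 10.3 announces.
- Log patients converted before opening as consented but not randomised. Fix in advance what happens to their unopened serial number, for example retired unopened or passed to the next patient.
- Beside 11.8, state that outcomes continue to be collected on patients converted after opening and that these patients are analysed in their assigned arm. This closes the separate gap that exists under either reveal time.

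The criteria for conversion are left as they are. The cost is a few sentences in 10.3, 11.1(2), 11.2 and 11.8, and one log. If 130 counts consented patients, slightly fewer will be assigned; the protocol should say which count it means.

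### No blocking or stratification by operating surgeon is described, and the surgeon is neither recorded nor used in the analysis; if several surgeons operate, this adds avoidable noise, though not bias

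*Combined protocol and SAP*

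**What the plan says.** All references are to the combined protocol and SAP.

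- **Generation.** Section 10.3 begins "The anastomosis method will be determined preoperatively using a" and then offers a random table or a computer program as alternatives. It leaves the process to consultation with a research institute. Section 11.2 names SAS, run by the hospital's MRCC: "A random number will be generated, assigned a serial number, and the anastomotic method will be delivered just before surgery". The ratio is 1:1 and the target is 65 per group. No section mentions blocks, strata, minimisation or the surgeon.
- **Time of disclosure.** Section 10.3 has the group revealed in theatre, immediately ahead of the anastomosis. Sections 11.1(2) and 11.2 place it ahead of the operation.
- **Data items.** The intraoperative items in 11.1(4) are "operative time, intraoperative blood loss". The operator appears neither there nor elsewhere in the list.
- **Analysis.** Section 11.11 lists t, Mann-Whitney, chi-square and Fisher tests, with a general option to seek advice on advanced methods.
- **Operators.** Section 3 lists a principal investigator and co-investigators, with the affiliation "Department of Surgery, Bundang Seoul National University Hospital". The plan does not say how many surgeons perform the trial operations.
- **Comparability.** Section 11.1(2) says that the groups will be handled alike apart from the anastomosis. It does not mention the operator.

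**The concern.** The surgeon delivers the intervention, and may plausibly influence complications and speed of recovery. Freedom from major complications is one of the conditions for recovery in the primary endpoint (11.4). There are three usual ways to deal with the operator: stratify the allocation, record who operated, and account for it in the analysis. The plan describes none of them.

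At stake is some precision in the comparison of 7-day recovery, complications and length of stay. So is the ability to show, from the trial's own data and by a rule fixed in advance, that operators were evenly spread.

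The conflict over disclosure time is a related matter. If the technique is known before the operation starts, the choice of operator could follow the allocation. That would be systematic rather than chance imbalance, and a trial data set without the operator would not show it.

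**Working it through.** **1. The plan's own figure.** Inputs from 10.3: 90% v 70%, "Type I error (α): 5"%, power 80%, ratio 1:1, dropout 10%. Sidedness is not stated; two-sided is assumed. With unpooled variance, n = (1.960 + 0.842)² × (0.90×0.10 + 0.70×0.30) / 0.20² = 7.849 × 0.30 / 0.04 = 58.9, so 59 per arm. Then 59 × 1.1 = 64.9, so 65 per arm and 130 in total. The figure reproduces.

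**2. Chance imbalance in one surgeon's share.** Assumptions: k surgeons with equal volume (share q = 1/k), no stratification, about 65 per arm. The between-arm difference in a specified surgeon's share has SD = √[q(1−q)(1/65 + 1/65)]. The simulated columns come from 20,000 trials of 130 patients, with simple allocation and with a forced 65/65 split.

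| Surgeons | SD (points) | P(≥10 points), normal | P(≥10), simulated | P(≥15), simulated |
|---|---|---|---|---|
| 2 | 8.8 | 25% | 26% | 9% to 10% |
| 3 | 8.3 | 23% | 23% | 7% to 8% |
| 4 | 7.6 | 19% | 18% to 19% | 5% |

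Forcing 65/65 barely changes these figures, so blocking that ignores the surgeon would not solve the problem. Balancing within surgeon brings the imbalance to about zero.

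**3. Effect on the treatment difference.** Shift = imbalance in share × gap in recovery rate between that surgeon and colleagues. The plan gives no gap. For an assumed 15 points:

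- 0.10 × 0.15 = 1.5 points
- 0.15 × 0.15 = 2.25, about 2.3 points

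At the 95th percentile of imbalance for two surgeons (about 17.2 points), gaps of 5, 10 and 20 points give shifts of 0.9, 1.7 and 3.4 points.

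**4. Comparison with sampling error.** The standard error of the 90% v 70% difference with 65 per arm is √(0.30/65) = 6.8 points. A 15-point surgeon gap with two surgeons adds a component with SD 0.15 × 8.8 = 1.3 points.

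**5. Error rate and power.** Simulation with two equal-volume surgeons, 116 evaluable patients (130 less about 10%), 8,000 replicates; simulation error is about 0.4 to 0.5 points on each power figure.

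| Surgeon gap | Type I error, unstratified list, chi-square | Power, unstratified list, chi-square | Power, stratified list, CMH |
|---|---|---|---|
| 0 | 5.3% | 78.7% | 78.9% |
| 10 points | 5.0% | 78.5% | 80.1% |
| 20 points | 5.1% | 78.8% | 81.9% |

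The 20-point row is extreme: it puts the two surgeons at 100% and 80% in one arm and at 80% and 60% in the other. Adjusting for surgeon without stratifying the list gives 81.2% in that row, so most of the gain comes from recording the surgeon and using it in the analysis.

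**The case against.** The strongest reply is that randomisation already protects against operator confounding in expectation, so stratifying by surgeon is a design option and not the repair of an error. That stands. The shift is small beside the 6.8-point standard error, and there is little or no power to gain unless surgeons differ widely.

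Four stronger readings are tempting, and the documents do not support them.

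- **That allocation is unrestricted.** This would be inferred from silence. Blocks are neither stated nor excluded, 65/65 is a target, and the process is left to consultation. What can be said is that no restriction is described. Simple allocation would also cost little: at a 54/76 split, the edge of its 95% range, power is 80.1%, against 82.1% at 65/65 before dropout.
- **That imbalance could never be seen or corrected.** The operator can probably be recovered from operative records, although this too is an assumption. Such an adjustment would be post hoc. The monitoring in 11.10 cross-checks records for one participant, so it does not fill the gap.
- **That several surgeons operate.** Investigator status does not show who operates. With a single operator the point falls away.
- **That the chance of harm is above 40%.** With three surgeons, the probability that any one of them is out of balance by 10 points or more is about 42% to 46%. The shift in step 3 needs the imbalance to fall on the surgeon whose results differ, so the figure for a specified surgeon is the relevant one.

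Blocking within surgeon also makes allocation somewhat easier to guess in an unmasked surgical trial. That is a real cost, and varying block sizes limit it.

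**Conclusion.** The point holds as a modest and inexpensive improvement. No restriction by surgeon is described, the surgeon is not a listed item, and no surgeon-adjusted analysis is planned. If two or three surgeons share cases equally, a specified surgeon's share differs between arms by 10 points or more with probability about 23% to 26%. With a 15-point gap in recovery rate, an imbalance of 10 to 15 points moves the result by about 1.5 to 2.3 points of the planned 20. This is noise: type I error stays about 5%, and handling the surgeon in design and analysis gains about 3 points of power at a 20-point gap and between nothing and 2 points at a 10-point gap.

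The number of surgeons, their volumes and the gaps between them are assumptions. The inconsistent disclosure time does not depend on them and needs reconciling in any case.

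**What to change.** 1. **11.1(4):** add operating surgeon to the intraoperative findings. Cost: one case-report field. This is worth doing even if stratified allocation is declined.
2. **11.2:** state how many surgeons operate and what restriction the list uses. If more than one operates, have the MRCC generate the list stratified by surgeon, in permuted blocks of randomly varying size (for example 4 and 6) not disclosed to the surgeons. Cost: a few lines of SAS. If one surgeon performs every case, say so; no stratification is then needed.
3. **11.11:** if more than one surgeon operates, pre-specify a Cochran-Mantel-Haenszel analysis of 7-day recovery stratified by surgeon.
4. **10.3 and 11.2:** name one generator and drop the random-table alternative.
5. **10.3, 11.1(2) and 11.2:** reconcile the moment at which allocation is revealed, and require the operator to be fixed and recorded beforehand, so that the choice of operator cannot follow the allocation.

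No extra patients or staff are needed, and 130 stands.
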